8 STUDY MATERIALS

8.1 Study treatments

The investigational product (IP) is CSF-1.

CSF-1, a sterile topical eye drop solution. The formulation developed by Orasis Pharmaceuticals Ltd. is a preservative-free eye drop, containing the active ingredient pilocarpine hydrochloride 0.4%, with the addition of standard pharmacopeial excipients used in sterile ophthalmic solutions.

The vehicle (CSF-1 placebo) is a topical eye drop solution containing the same ingredients as in CSF-1 except for the active ingredient.

Both CSF-1 and vehicle are packaged in single-dose transparent low-density polyethylene (LDPE) vials, enclosed within a pouch. Each pouch includes five vials. CSF-1 will be evaluated for comparison to vehicle.

8.1.1 Instructions for Use and Administration

CSF-1 or vehicle are topical ophthalmic solutions that should be administered bilaterally. Subjects will be instructed to instill with a single drop in each eye twice daily (BID). The first daily dose should occur in the morning, with the second dose following approximately 2 to 3 hours later. Subjects should be reminded not to dose at home on clinic visit days.

8.1.2 Subject Instructions

After obtaining written informed consent, Subjects will be screened at Visit 1. At Visit 2 subjects will be randomized and will receive study drug and a paper dosing diary.

Subjects will be instructed to instill a single drop of study drug in each eye twice daily (BID). The first daily dose should occur in the morning, with the second dose following approximately 2 to 3 hours later and subjects should record each dosing time in their diary.

Subjects should not dose on the AM of each visit. At each visit, subjects will receive their AM dose at the visit by study personnel after their visual assessments are completed.

Subjects will be instructed that study drug must be stored in a refrigerator between 2° to 8°C (36° to 46°F). An open vial should never be re-used. Subjects will be instructed to save all used vials and return all used vials and unused study drug kits to next study visit for a compliance check.

At Visit 4 or the next scheduled study visit, subjects will return to clinic to complete exit visit assessments. Study drug (used and unused vials) and diary will be collected from all subjects. All subjects who have not completed Visit 4 (Week 6) at the time of Protocol Amendment 2.0 approval will exit the study after all assessments are complete at Visit 4. All subjects treated beyond Visit 4 at the time of Protocol Amendment 2.0 approval will exit the study after all assessments are complete at the next scheduled visit ([REDACTED]).

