A total of 309 subjects with presbyopia were randomized in NEAR-1 (155 CSF-1 and 154 vehicle) and 304 were randomized in NEAR-2 (154 CSF-1 and 150 vehicle). Participants were treated BID (with an interval of 2 or 3 hours between both doses) with 1 drop of CSF-1 in each eye, for a period of 15 days. Efficacy parameters (Best Distance Corrected Visual Acuity (BDCVA) at 40cm and 4m, as well as pupil diameters) were measured on day 1, 8 and 15 at various time points during these days. The primary and key secondary end-points were the percentage of subjects with a ≥ 3 -line (15-letter) gain, from baseline, in BDCVA at 40 cm (Precision Vision chart) and no loss in BDCVA ≥ 5 letters (ETDRS

chart at 4 m) in the study eye on Day 8, 1 hour post dose 1 (primary end-point) and on the same Day 8, up to 4h post dose 1. The other secondary endpoints were the same endpoints but measured on Day 1 (up to 6h post dose 1) and on Day 15 (up to 8h post dose 1).

In both NEAR-1 and NEAR-2 studies, CSF-1 showed a statistically significant superior effect compared to vehicle in all primary and key secondary endpoints (all time points on Day 8 [from 1 hour post-dose 1 to 2 hours post-dose 2]). The superiority of CSF-1 compared to vehicle, was also demonstrated on Day 1 and on Day 15. The pooled data of NEAR-1 and NEAR-2 showed a statistically significant superior effect in all time points on Day 1 and Day 15.

In both Phase 3 studies, the safety endpoints of Slit-Lamp Biomicroscopy, BDCVA, Intraocular Pressure, and Conjunctival Redness, changes from baseline were found to be comparable between the CSF-1 and vehicle groups. On a drop comfort scale from 0 (very comfortable) to 10 (very uncomfortable), mean scores were <2 at all timepoints, indicating that CSF-1 was well tolerated.

The current safety study is initiated to evaluate the safety of CSF-1, administered twice a day (BID) with an interval of 2-3 hours.

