5.1 Dose Regimen

Enrolled subjects will be randomized 2:1 to receive CSF-1 or vehicle bilaterally. Subjects will be instructed to dose one drop in each eye, twice daily (BID), at 2 to 3 hours intervals (OU). This regimen should be followed daily. Subjects who have not completed Visit 4 (Week 6) at the time of Protocol Amendment 2.0 approval will dose for at least 6 weeks. Subjects treated beyond Visit 4 at the time of Protocol Amendment 2.0 approval will dose until the next scheduled visit (████████) and exit the study. Subjects must avoid dosing prior to visit on the day of a visit. If subjects dose prior to their visit, the study visit will be rescheduled.

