11.6 Safety Analysis

All safety data will be analyzed using the safety set. Safety of CSF-1 compared to vehicle will be assessed by the review of all safety parameters.

Verbatim descriptions of AEs will be mapped to Medical Dictionary for Regulatory Activities (MedDRA) terms and be presented in a data listing. Treatment emergent AEs (TEAEs) is defined as any event not present prior to the initiation of the drug treatment or any event already present that worsens in either intensity or frequency following exposure to the drug treatment. TEAEs will be summarized by treatment group using frequency and percent for each system organ class (SOC) and preferred term (PT) within each SOC. The

number of AEs, TEAEs, serious TEAEs, and TEAEs causing premature discontinuation will be provided by treatment group. In addition, the frequency and percentage of subjects with at least one AE, at least one TEAE, and at least one serious TEAE will also be provided by treatment group.

Similar summaries will also be presented for TEAEs related to the study drug, by severity, and by study day of onset. When reporting the incidence of AEs, a subject will only be counted once if they ever experience an event within the SOC and ever experience the individual PT within each treatment group. The number of AEs as well as the incidence rate over the study period will also be summarized.

Changes from baseline in vital signs, BDCVA, LL-BDCVA, slit lamp biomicroscopy, IOP, and dilated indirect fundus examination and endothelial cell density will be summarized descriptively for at each visit by treatment group. Changes from baseline in endothelial cell density parameters will be tested between treatment groups using two-sample t-tests.

The categorical summaries for the loss of ≥ 0.2 logMAR from baseline (yes/no) and for the loss of > 0.2 logMAR (yes/no) in BDCVA and LL-BDCVA at each visit will also be presented and compared between treatment groups using Pearson chi-squared test or Fisher's exact test if any cell counts are less than 5.

Full details of the safety analyses will be specified in the formal Statistical Analysis Plan.

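### Does reading LL-BDCVA before the visit-day dose mean the acuity-loss comparison in section 11.6 has to change?

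*Combined protocol and SAP*

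**What the plan says.** **Order of dosing and assessment.** Section 8.1.2 places the visit-day dose last: "At each visit, subjects will receive their AM dose at the visit by study personnel after their visual assessments are completed". Section 5.1 backs this up: "If subjects dose prior to their visit, the study visit will be rescheduled". Section 5 has the same order at Visit 2, with the first dose given once acuity has been assessed. Section 11.1 takes baseline from before the first dose.

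**Daily schedule.** Section 8.1.1: "The first daily dose should occur in the morning, with the second dose following approximately 2 to 3 hours later". Section 8.1.2 adds that "subjects should record each dosing time in their diary".

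**Earlier evidence of effect.** Section 3 says that further secondary endpoints in NEAR-1 and NEAR-2 were "measured on Day 1 (up to 6h post dose 1) and on Day 15 (up to 8h post dose 1"), and that the pooled data "showed a statistically significant superior effect in all time points on Day 1 and Day 15".

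**Analysis.** Section 11.6 says that losses of at least 0.2 logMAR, and of more than 0.2 logMAR, "in BDCVA and LL-BDCVA at each visit will also be presented and compared between treatment groups". On the overall judgement it says: "Safety of CSF-1 compared to vehicle will be assessed by the review of all safety parameters". It leaves full detail to the formal SAP.

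**The concern.** CSF-1 works by constricting the pupil, so low-luminance acuity is a natural place to look for harm while the drug is acting. In the visible text, every follow-up reading is taken before that day's dose, well past the last time at which section 3 reports an effect. Section 11.6 does not call the readings pre-dose and plans no summary of time since the last drop, although the diary records dosing times. It also feeds every safety parameter into the overall judgement without qualification.

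The risk is over-reading. If few or no subjects on CSF-1 lost 0.2 logMAR, a reader could take this as reassurance about low-light vision on the drug, when the data speak to acuity roughly a day after the last drop.

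**Working it through.** **1. The plan's own figure.** The synopsis gives at least 95% probability of seeing an adverse event of true rate 2.66% among 113 CSF-1 subjects. Check: 1 − (1 − 0.0266)^113 = 0.9525. It reproduces. It concerns adverse events and does not depend on when acuity is read.

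**2. Time from last drop to reading.** The last drop is the previous day's second dose, so interval = 24 + clock time of reading − (clock time of first dose + 2 to 3 h). The documents give no clock times beyond morning, so the times below are assumptions.

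| First dose | Reading | Shortest | Longest |
|---|---|---|---|
| 06:00–12:00 | 08:00–16:00 | 24 + 8 − 15 = 17 h | 24 + 16 − 8 = 32 h |
| 06:00–12:00 | 08:00–12:00 | 17 h | 24 + 12 − 8 = 28 h |
| by 12:00 | any time next day | 24 + 0 − 15 = 9 h | – |

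The 32 h end needs an afternoon reading, which sits poorly with a morning dose given at the visit.

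**3. Against the earlier trials.** Eight hours after dose 1 is 8 − 3 = 5 h to 8 − 2 = 6 h after dose 2. Even the 9 h minimum is later than that. But 8 h is the last time described, not a shown end of effect, and the endpoint was near-vision gain without distance loss. Some residual effect at trough is not excluded.

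**4. What a null result would bound.** For 0 losses in 113 subjects, the 95% upper limit is 1 − 0.05^(1/113) = 2.62% (one-sided) or 1 − 0.025^(1/113) = 3.21% (two-sided exact). For 0/113 against 0/57, the Wilson upper limits are 3.84/(113 + 3.84) = 3.29% and 3.84/(57 + 3.84) = 6.31%. The Newcombe 95% interval for the difference is therefore −6.31 to +3.29 points. These limits are per subject and apply to trough readings. The plan proposes none of them, and section 11.2 analyses both eyes.

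**5. What would move the answer.** Suppose the vehicle loss rate is 2% (assumed). If readings were taken post-dose and the CSF-1 rate were 15% or 20%, the planned test at 113 against 57 would have about 79% or 96% power (exact enumeration). If the effect has gone by trough (2% in both arms), it rejects about 2% of the time. The gap between these figures comes entirely from when acuity is read. Labelling the readings pre-dose, or tabulating hours since the last drop, leaves every one of them unchanged.

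**The case for a change.** The strongest case for a change is this. Safety is the trial's only objective. Section 3 describes no low-luminance acuity in the NEAR trials, so this trial is the only source of it in the visible documents. A pre-dose label, a caution about null results and a table of hours since dosing would cost little and could prevent a mistaken claim.

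What stands is the factual core: the visible readings are pre-dose, and the comparison does not directly measure low-light acuity during drug action. A stronger statement, that a null result is no evidence at all about that period, is not supported, because residual effect at trough is not excluded.

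The rest gives way on five points.

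- The timing is stated in the synopsis and in sections 5, 5.1 and 8.1.2. An analyst working from the protocol will know the readings are pre-dose and can say so in the report.
- For ordinary distance acuity the gap is narrower still. Section 3 reports 4 m acuity in the NEAR trials at post-dose times, a responder definition that excluded a loss of 5 letters or more, and comparable safety BDCVA changes between arms.
- The plan makes no on-drug low-light claim and no confidence bound. Visual symptoms during drug action can still be captured as reported, elicited or observed adverse events.
- The table would mostly confirm an interval that the schedule already fixes. The diary is on paper, and no visible text says its times, or the clock time of each acuity reading, reach the database.
- The ordered visit procedures are redacted, Appendices 1 and 2 are not shown, and the formal SAP is not in the supplied text. A post-dose reading or a label could be in any of these, and redaction is not omission.

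**Conclusion.** No change is needed. Follow-up LL-BDCVA in the visible text is a trough measurement, at least 9 h after the last drop if the first dose is taken by noon and the second within 3 h of it, and 17 to 32 h under the assumed clinic hours. Comparing drug-free follow-up with drug-free baseline is a coherent test of persistent or cumulative change, which is a fair question for a safety study with repeated dosing.

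The wording gap in 11.6 is one that analysts fill sensibly from the dosing sections, and filling it alters no test, estimate or error rate. Only a timed post-dose LL-BDCVA reading would let the trial answer the on-drug question. That is an added procedure, to be weighed against masking (the miosis is visible), the dilated fundus examination and visit length. Leaving it out is a fair trade-off.

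This conclusion rests on the visible text. If the redacted procedures or the SAP contain a post-dose reading, the concern falls away, provided it is clear which reading the loss comparison uses.

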6.5 Withdrawal Criteria

Subjects will be withdrawn from the study if any of the following criteria are met:

- Be a female of childbearing potential who is currently pregnant, nursing, or planning a pregnancy; tests positive to a urine pregnancy test or refuses to use an adequate method of contraception for the duration of the study;
- Have an active ocular infection (bacterial, viral, or fungal), active ocular inflammation (e.g., moderate to severe blepharitis, allergic conjunctivitis, peripheral ulcerative keratitis, scleritis, uveitis) at any visit in either eye.
- Subjects may also be withdrawn from the study for the following reasons:
 - Adverse event (AE)
 - Lost to follow-up
 - Withdrawal of consent by subject
 - Investigator's discretion
 - Death
 - Subject not adequately following required study procedures
 - Study terminated by the Sponsor
 - Other

Subject withdrawals will be documented on the subject's source document.

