9.4.2 Unscheduled Visits

In the case of an AE, an unscheduled visit may occur. The investigator may perform additional assessments at their discretion. All additional assessments will be documented in the subject's source document.

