11 STATISTICAL HYPOTHESES AND METHODS OF ANALYSES

11.1 General Considerations

In general, quantitative/continuous data will be summarized using descriptive statistics (number of subjects [n], mean, standard deviation [SD], median, minimum, and maximum).

Qualitative/categorical data will be summarized using frequencies and percentages. Statistical testing, unless otherwise indicated, will be performed at a 2-sided 0.05 significance level.

For all variables, baseline is defined as the last measurement taken prior to the administration of the first dose of study drug. Change from baseline will be calculated as follow-up measure minus baseline measure.

Summaries and listings will be presented for all subjects, or safety set, as needed. Safety analyses will be conducted in the safety set.

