11.2 Analysis Sets

- Safety Set – The safety set will include all randomized subjects who have received at least 1 dose of the study drug. Subjects in the safety set will be analyzed as treated and will be used for the safety analyses. No data will be excluded for any reason.
- Unit of Analysis

Both eyes will be displayed and analyzed for all ophthalmic safety variables.

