11.4 Sample Size

Approximately 170 subjects will be randomized into the study in a 2:1 ratio of CSF-1:vehicle [approximately 113 randomized subjects assigned to CSF-1 and approximately 57 subjects randomized to vehicle] completing at least 6 weeks of treatment. Any subjects treated beyond Visit 4 at the time of Protocol Amendment 2.0 approval will exit the study at the next scheduled visit. All subject data will be analyzed.

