11.8 Missing Data

There will be no imputations for missing data.

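### Could acuity loss measured at an unscheduled adverse-event visit distort, or drop out of, the by-visit loss comparisons?

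*Combined protocol and SAP*

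**What the plan says.** **When acuity is tested.** Section 8.1.2 of the protocol reads: "At each visit, subjects will receive their AM dose at the visit by study personnel after their visual assessments are completed". Sections 5.1 and 8.1.1 support this: subjects are not to dose at home before a visit that day, and a visit is rescheduled if they do. None of these sentences is limited to scheduled visits. Section 11.1 fixes the reference value before treatment: "baseline is defined as the last measurement taken prior to the administration of the first dose of study drug".

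**Unscheduled visits.** Section 9.4.2 reads: "In the case of an AE, an unscheduled visit may occur. The investigator may perform additional assessments at their discretion". It names no acuity test and no timing relative to the drop, and it names only the source document as the place of record.

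**Analysis.** Section 11.6 says that losses of ≥0.2 and >0.2 logMAR "in BDCVA and LL-BDCVA at each visit will also be presented and compared between treatment groups", by Pearson chi-squared or Fisher's exact test, and defers full detail to a formal SAP. Section 11.2 adds "No data will be excluded for any reason" and Section 11.4 adds "All subject data will be analyzed". On missing values, Section 11.8 states: "There will be no imputations for missing data".

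**The concern.** Scheduled acuity is measured before the day's first dose, so the planned comparisons address loss that persists to the next dose. A subject who comes in because vision blurred after a drop has probably already dosed. Acuity tested then reflects acute change against a pre-dose baseline, which is a different quantity.

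If such values enter a by-visit comparison, acute and persistent change are mixed, and more so in the arm with more adverse-event visits. If they do not, the loss tables can show zero although losses were measured. Section 6.5 ("Subjects may also be withdrawn from the study for the following reasons") lists an adverse event among those reasons. A subject who left for that reason would have no later scheduled value, and nothing is imputed. Safety is the only objective, so one would not want the counting rule chosen after the data are seen.

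**Working it through.** **1. The plan's own figure.** Inputs from the Synopsis, Sample Size: 113 CSF-1 subjects and an event rate of 2.66%. The chance of seeing at least one event is 1 − (1 − 0.0266)^113 = 0.9525, which agrees with the stated minimum of 95%. The split also agrees: 170 × 2/3 = 113.3 and 170 × 1/3 = 56.7. The concern does not depend on this figure. It supplies the arm sizes and a scale: 0.0266 × 113 = 3.0 subjects.

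**2. The sections side by side.**

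- *Dose timing.* The visit-day rule in Sections 5.1, 8.1.1 and 8.1.2 is worded for visits in general. Read literally it can cover an unscheduled visit, so it would be too strong to say that no timing rule exists. The text does not say whether the rule is meant for visits prompted by an adverse event.
- *Data inclusion.* The Section 11.4 sentence on analyzing all data follows directly on the subjects treated beyond Visit 4. Section 5 gives the fuller version, covering all measured timepoints including those subjects. The Section 11.2 sentence sits in the definition of the safety set. Neither conflicts with a table by scheduled visit that has the other values listed beside it.
- *Where a measured loss goes.* Section 10.1 treats clinically relevant worsening of findings as an adverse event, and sends events revealed by examination or diagnostic procedures to both source document and eCRF. Section 11.6 then tabulates treatment-emergent events by arm, severity and relatedness. Section 12.6 separately requires complete study data in the eCRF.
- *Early leavers.* Section 9.6.3 asks sites to gather what follow-up they can before a subject is discontinued.

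**3. Size, by assumption only.** The documents give no rate of unscheduled acuity tests or of losses found there. Let k of 113 CSF-1 subjects have a loss seen only at an unscheduled post-dose test, with 0 of 57 on vehicle and no scheduled losses. Left out, the table reads 0% against 0%. Counted, with two-sided Fisher's exact test:

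| k | k/113 | p against 0/57 |
|---|---|---|
| 3 | 2.65% | 0.55 |
| 5 | 4.42% | 0.17 |
| 8 | 7.08% | 0.053 |
| 9 | 7.96% | 0.030 |

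The exact 95% interval is 0.6% to 7.6% at k = 3 and 3.7% to 14.6% at k = 9. With one loss on vehicle, k = 12 gives p = 0.0625 and k = 13 gives p = 0.036.

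The table puts all k losses into a single comparison, which is the least favorable case, because Section 11.6 compares at each visit. If nine losses fall 5 and 4 across two visits, the p-values are 0.17 and 0.30.

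**The case for a change.** The strongest argument for a change is this. Acuity loss is one of only two outcomes with a between-arm test in Section 11.6; the other is endothelial cell density. Section 9.4.2 names only the source document, whereas Sections 9.2, 10.1 and 10.3.2 name the eCRF as well, and a value kept only in source cannot reach a table. Even where no test result changes, 0% against 2.7% is a visible difference in a safety report, and it matches the event rate the study is sized to detect. The remedy would be cheap: two sentences, a small descriptive table and one eCRF item.

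Part of this stands. No readable section maps an unscheduled acuity value to the by-visit comparisons. The visit-day dosing rule also sits awkwardly with Section 9.4.2, since read literally it would reschedule an adverse-event visit because the subject had dosed. Which reading is intended is for the sponsor to say.

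The rest is weaker. A measured loss that matters clinically is reported as an adverse event by arm, and Section 12.6 already covers the eCRF point. The p-value decides nothing formally: Section 11.6 judges safety by reviewing all parameters, and Section 11.9 makes no multiplicity adjustment. An any-time loss table would depend on who chose to come in. It would add a description but correct no wrong result. Section 3 reports that both earlier Phase 3 studies measured distance acuity after dosing and found safety BDCVA changes comparable between arms.

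**Conclusion.** This is a gap that analysts fill sensibly, and no change to the plan is called for. The natural reading of a by-visit comparison is scheduled visits. An unscheduled visit has no common visit label and no per-arm denominator, so values from it belong in listings and, where clinically relevant, in the adverse-event tables. A line confirming this would fit the SAP to which Section 11.6 defers.

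The effect cannot be estimated from the documents. Under the assumed counts, up to eight CSF-1 losses seen only at unscheduled tests would alter a displayed percentage but not the test result. Nine would be needed to alter the result, with none on vehicle, none at scheduled visits and all in one comparison.

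The conclusion rests on the readable text. The visit-by-visit procedures (Section 9.3.1), the visit schedule (Appendix 1) and the examination methods (Appendix 2) are redacted or not shown, and no separate SAP text is available here. Any of these may already settle both the timing and the mapping.
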